**Table 2 Time schedule during confinement at PET centre/CPU (Visit 4, Day 8 (Panel A))**

Protocol time (hh:mm)	Administrati on of SQL SR once daily in the morning	Adm of (S,S)[  F]FM eNER-D 2 IV solution a	PET exami- nation a	Blood sampling for quetiapine PK	Vital signs	Bond- Lader VAS	Other
Pre-dose				X b	X c	X d	Light breakfast (approx. 2 h before dose)
00:00 (~9am)	X						Transfer to PET centre
01:00				X			
02:00				X			
03:00				X			
03:30		X					
04:00				X			Light meal
05:00				X			
06:00				X			
07:00			↓	X			Transfer to CPU
08:00				X			Dinner
10:00				X			
12:00				X			
24:00				X			

- a) Time of PET and administration of (S,S)[F]FM eNER-D2 IV solution is tentative.  
b) Blood sample for quetiapine PK analysis to be taken 15 min before administration of SQL SR.  
c) Vital signs includes pulse, systolic and diastolic blood pressure supine and again 2 min after standing.  
d) Bond-Lader VAS should be in the morning pre-dose.

[figure not shown]
**Figure 1 Study flow chart**

**Panel A: 300mg SQL SR**

Cx is the quetiapine plasma concentration at the time of PET measurement. This will be assessed at the expected time of Cmax.

**During PET examination day**

**3.2 Rationale and risk/benefit assessment**

**3.2.1 Rationale for study design, doses and control groups**

In a study where the primary objective is to determine the occupancy of NET induced by quetiapine an open study is deemed sufficient.

The present study will be conducted in healthy male volunteers. The PET study requires to be performed in antipsychotic treatment-naïve subjects. Since patients requiring anti-psychotic therapy can rapidly destabilise and may have a relapse of symptoms when their anti-psychotic medication is stopped during the medication washout periods, it is considered inappropriate to

enrol such patients. Moreover it is also considered inappropriate to treat them with the SR doses proposed in this study, as they were not evaluated in the clinical program of SQL SR in patients with schizophrenia. Previous AstraZeneca studies have not shown any differences in pharmacokinetics of quetiapine between healthy and patient populations. Thus, it is presumed that NET occupancy of quetiapine in healthy volunteers will be representative of its binding to NET in human brain in vivo. Furthermore as many Central Nervous System (CNS) disease states to be studied with SQL SR will occur in antipsychotic treatment-naïve patients, healthy volunteers are thought to serve as an appropriate surrogate for the first study determining NET occupancy in man.

The doses that will be explored are those currently being evaluated in the MDD clinical program, 50 mg to 300 mg. The safety and tolerability of the doses selected in the present study and of a previous slightly quicker dose escalation scheme than currently proposed have been previously characterised in healthy volunteers and in patients with schizophrenia, schizoaffective disorder and bipolar disorder ([Investigator's Brochure, SEROQUEL™, 2007](#)). Necessary precaution to ensure the safety of the healthy volunteers will be taken (see 3.2.2). The PK characteristics of the doses chosen have also been characterized in healthy volunteers and/or in patients ([Investigator's Brochure, SEROQUEL™, 2007](#)): plasma quetiapine concentration time-profiles at oral doses of 50 mg, 150 mg and 300 mg: median time of  $C_{max}$ ,  $T_{max}$  is 6 hours,  $T_{1/2}$  is 6 hours post-dose. Plasma NDAQ concentration time-profiles:  $C_{max}$ , reaches  $T_{max}$  at 6 hours post-dose ([Investigator's Brochure, SEROQUEL™, 2007](#)).

The PET method is chosen for the study, as the molecular imaging method with highest image resolution (as compared to SPECT) and radioligand availability for the investigation of noradrenaline system. The radioligand (S,S)[F]FMENR-D2 will be used for the study, as it has the favourable pharmacokinetics (it reaches equilibrium) and shows high specific binding in thalamus, brainstem regions (locus coeruleus). These characteristics of the ligand enable application of quantitative methods that are needed to evaluate NET occupancy induced by quetiapine/NDAQ. Presently, it is the only radioligand available that provides such possibility.

### **3.2.2 Risk/benefit and ethical assessment**

The aim of this study is to investigate if SQL SR at doses from 50 mg to 300 mg induces NET occupancy in healthy volunteers. Determining NET occupancy in vivo in human may reveal important mechanism of action for the antidepressant properties of SQL. Investigation of noradrenaline transporter as a target may also be important lead for the development of antidepressant drugs, beneficial for the patients and society at large.

The PET experimental procedures carry low risks. The administered maximum radioactivity is chosen as guided by the possibility to quantify the radioligand binding to NET (limited by the measurement signal-to-noise ratio). The total radioactivity will be maximum 375 MBq (approximately 185 MBq per injection) (following radiation safety requirements in EU ([Annals ICRP 1987](#)), max 10 mSv per year).

Subjects who have previously been administered PET radioligands cannot participate in this study, in accordance with the routines established by the local radiation safety committee. The

risk posed by radioactivity exposure is considered acceptable in relation to the potential benefits. The procedure-related risks are few. The venipuncture may cause some pain. The PET procedure requires that subjects rest in the supine position with the head fixated inside the opening of the PET camera system. Possible physical discomfort due to restriction of movement or local pressure is usually alleviated by loosening and cushioning of the fixation system. The subjects are accompanied in the examination room throughout the procedure.

It is concluded that the exposure levels of (S,S)[F]FMeNER-D2 micro dose and radioactivity as well as the study procedures defined in this protocol are not expected to pose any significant risks that cannot be monitored in the study.

The doses of SQL SR that will be administered have been previously evaluated in healthy volunteers ([Investigator's Brochure, SEROQUEL™, 2007](#)). In the studies the safety profile of SQL SR was acceptable and consistent with the known profile for SQL. There were no unexpected adverse events. Side effects are somnolence, dizziness and orthostatic hypotension. The side effects are reversible and do not put the subject to a serious risk. The escalated dosing of the SQL SR will be slightly slower than previously studied. Healthy volunteers will remain hospitalized and monitored throughout the period of treatment. In order to further ensure the safety of the healthy volunteers and avoid orthostatic hypotension related side effects, healthy volunteers will be instructed to be cautious when standing up and close medical monitoring will be observed when orthostatic blood pressure will be assessed. In addition a nurse from the CPU will accompany and monitor/assist the subjects during transportation between the CPU and the PET centre and at the PET centre.

The MRI investigations are clinical routine investigations with strict safety protocols to assure that subjects do not have any contraindications for the procedure such as magnetic metallic implants. The MRI staffs are specifically trained and there are specific routines to handle these types of unusual complications. Overall, the MRI investigations involve very low risk and the results of the investigations are crucial for the study, both for ensuring inclusion criteria and to correctly analyse the PET-data.

There are no direct benefits for healthy volunteers participating in the study. The risk is judged to be minor, all investigational procedures are otherwise routinely used in clinical medical investigations. The ethical assessment is of course also dependent on provision of informed consent and reviews by local ethical committee as well as local radiation protection committee.

### **3.3 Selection of study population**

#### **3.3.1 Study selection record**

Investigator(s) must keep a record of subjects who were considered for enrolment but never enrolled e.g., subject screening log, according to local procedures. This information is necessary to establish that the subject population was selected without bias.

Subjects will be enrolled and undergo a screening visit at AstraZeneca CPU within the 30 days preceding the first PET examination.

### **3.3.2 Inclusion criteria**

For inclusion in the study subjects must fulfil all of the following criteria:

1. Provision of a signed written informed consent.
2. Male healthy volunteers, aged 20 to 45 years inclusive, and judged to be healthy by the investigator on the basis of medical history, physical examination, ECG, vital signs, and laboratory tests (clinical chemistry, haematology, and urinalysis) at enrolment.
3. Weight of at least 50 kg and maximum 100 kg; Body Mass Index (BMI) of  $\geq 19$  to  $\leq 30$  kg/m^2.
4. Subjects are able to communicate with the investigator and to understand and comply with all requirements of study participation.
5. Negative results of the urine drug screen (amphetamines/ecstasy, benzodiazepines, cannabinoids, cocaine, opiates, and LSD).
6. Normal MRI scan at Visit 2.

### **3.3.3 Exclusion criteria**

Any of the following is regarded as a criterion for exclusion from the study:

1. A history or presence of neurological, haematological, psychiatric, gastrointestinal, hepatic, pulmonary, renal disease or other condition as judged by the investigator.
2. Trauma or sickness 2 weeks before the first PET examination, as judged by the investigator.
3. Intake of any prescribed medicine and over-the-counter (OTC) drugs (including herbals, vitamins and minerals), except for occasional paracetamol or adrenergic nasal spray, within 7 days before the first PET examination.
4. Use of drugs that induce the liver drug metabolising enzymes (including carbamazepine, phenytoin, barbiturates) or use of potent drugs that inhibit the cytochrome metabolising enzymes (e.g. Ketoconazole, itraconazole) within 4 weeks before first PET examination.
5. Consumption of liquorice or grapefruit-containing products within 7 days prior to Day 1.
6. Excessive use of caffeine (more than 5 cups of coffee or equivalent per day) within 7 days before first PET examination.
7. Habitual smoker (>5 cigarettes or snuff or other nicotine products per day).

8. Past or present drug or alcohol abuse, positive test results for drugs of abuse.
9. Positive test results for human immunodeficiency virus (HIV), hepatitis B (HBV) surface antigen (HBsAg), or hepatitis C antibody (HCV).
10. Donation of more than 400 mL of blood within 3 months prior to enrolment and 1200 mL 12 months prior to enrolment.
11. Plasma donation within two weeks prior to enrolment.
12. Participation in another study within 3 months before the start of the present study (or within 1 month for methodology studies in which no drugs were administered).
13. History of significant allergy.
14. Previous participation in a PET study (as required by the Radiation Ethics Committee).
15. Have had exposure to ionizing radiation that, in combination with the study, will exceed the ED limits.
16. Exposure to radioligand(s), which would result in a cumulative exposure that exceeds recommended EU exposure limits.
17. Subject suffer from claustrophobia.
18. Subject has implanted or embedded metal objects or fragments in the head or body.
19. Previous participation in and AstraZeneca Seroquel study.
20. Involvement in the planning and conduct of the study (applies to both AstraZeneca staff or staff at the investigational site).

#### **3.3.4 Restrictions**

Subjects will be required to:

1. On PET II examination day, subjects will be served breakfast approximately 2 hours prior to SQL SR intake, and will have light meal 4 hours after SQL SR intake, prior to PET-scanning procedure.
2. Refrain from the use of drugs that induce the liver drug metabolising enzymes (including carbamazepine, phenytoin, barbiturates) or use of potent drugs that inhibit the cytochrome metabolising enzymes (e.g. Ketoconazole, itroconazole) from enrolment and through the study period.
3. Refrain from consumption of liquorice and grapefruit containing products from 7 days prior to Day 1 through the study period.

4. Refrain from the use of any prescribed medicine and over-the-counter (OTC) drugs (including herbals, vitamins and minerals), except for occasional paracetamol or adrenergic nasal spray, from 7 days prior to PET (baseline) measurement and through the study period.
5. Abstain from drinking alcohol from 7 days prior to PET (baseline) measurement and through the study period.
6. On the PET examination days no caffeine or other stimulant drink intake is allowed until end of PET experiment. From 7 days prior to PET (baseline) measurement and through the rest of the study period the subject should abstain from excessive use of caffeine (more than 5 cups of coffee or equivalent per day).
7. Abstain from consumption of energy drinks containing taurine or glucuronolactone from enrolment and through the study period.
8. Refrain from the use of tobacco or other nicotine-containing products from enrolment through completion of the last PET examination.
9. Abstain from blood and plasma donation during the study and up to 3 months after completion of the study.
10. Refrain from strenuous physical exercise within 48 hours from PET (baseline) measurement and through the study period.
11. Subjects are to eat standardised meals during the residential period.
12. From first SQL SR dose and through the treatment period the subject will be instructed to be and should be cautious when standing up.
13. Subjects should on a daily basis drink at least a liter of water or other fluids in addition to what they drink with meals.
14. Male volunteers must refrain from fathering a child during the study and for three months following the study. Hence, they should not donate sperm and should ensure that their partners of child bearing potential use reliable method of contraception, as well as themselves using a barrier-method for this period.

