Thereafter, each healthy volunteer will undergo two PET examinations at two separate occasions at the [REDACTED]. The first PET examination is a baseline assessment of the distribution and density of noradrenaline transporter in the brain. After that, healthy volunteers will be confined to the AstraZeneca CPU during all days of SQL SR dosing, one of the days will also include a second visit to the PET centre. The second PET examination will be performed under SQL SR dosing (maintenance dose). The study will be concluded by a follow-up visit at the CPU five to nine days after the last SQL SR dose.

On the PET 2 examination the timing of the PET examination will be matched with the known PK parameters, median  $T_{max}$  of quetiapine and NDAQ after oral administration of SQL SR at 6 hours post-dose. For this reason the radioligand will be administered tentatively 3 and a half hours after administration of SQL SR and PET scanning time will be at 5-7 hours post-dose. A light meal (breakfast) approximately 2 hours prior to SQL SR administration will be given and a light meal will be given at 4 hours post dose. Monitoring of vital signs will be performed, prior to SQL SR intake.

In the unexpected event of technical failure (camera breakdown or the radioligand synthesis fails), the PET examination has to be moved to the nearest working day. In this case the SQL SR maintenance dosing period will be prolonged by 1-3 days (three days if it is moved from Friday to Monday). If this occurs the time the healthy volunteer are confined to the CPU will be prolonged.

Twelve serial blood samples will be obtained from each healthy volunteer between 15 min before administration of SQL SR and up to 24 hr after drug administration, at the second PET examination. The samples will be analysed for plasma concentrations of quetiapine and NDAQ. The aim is to take one sample at the start of the PET examination, one in the middle and one at the end of the PET examination.

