- c) In the unexpected event of technical failure (camera breakdown or the radioligand synthesis fails), the PET examination has to be moved to the nearest working day. Then it is done during the nearest days. In this case the SQL SR maintenance dosing period will be prolonged by 1-3 days (three days if it is moved from Friday to Monday). If this occurs the time the healthy volunteers are confined to the CPU will be prolonged.
- d) Vital signs includes pulse, systolic and diastolic blood pressure supine and again 2 min after standing.
- e) Vital signs will be assessed pre-dose and 6 hours post-dose during SQL treatment days, except for the PET 2 examination day, when vital signs will be assessed only pre-dose.
- f) ECG should be assessed prior to first titration dose, either day -1 or day 1.
- g) ECG should be assessed 6 hours post-dose the third day of steady state (maintenance dose).
- h) Blood sampling for a reduced Clinical chemistry/Haematology and Urinalysis should be repeated on the day of admission to the CPU if these samples were taken (at Enrolment visit) more than 1 week ago.
- i) Radioligand (S,S) [F]F MeNER-D2 to be injected 3.5 h (210 min) post-SRQ SR dose.  
PET measurements to start approximately 5 h post-SQL SR dose.
- j) Venous blood for PK analysis are to be taken 15 min pre-SQL SR dose, and 1, 2, 3, 4, 5, 6, 7, 8, 10, 12 and 24 h post-SQL SR dose.
- k) Bond-Lader VAS should be in the morning pre-dose.
- l) Training –Bond-Lader VAS
- m) Adverse Events (AEs) must be recorded from the admission to the CPU and until the follow up visit. Serious Adverse Events (SAEs) must be recorded from the time when the informed consent is obtained until the follow-up visit.

[figure not shown]

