#### **4.4.4 Bond-Lader Visual Analog Scale (VAS)**

This psychometric test will be collected at the times given in Table 1 to assess self-rated feelings. The first assessment upon admission to the CPU will be a training session to overcome practice effects and ensure optimal performance for the following assessments, which will take place pre-dose on the days of dosing of SQL SR and the day of discharge from the CPU. The second assessment on Day 1 (pre-dose) will be the baseline assessment.

The test being used for this study consists of a total of 16 100-mm lines anchored at either end by antonyms (Bond et al 1974). Participants mark their current subjective state between the antonyms on the line. Each line is scored as millimetres to the mark from the negative antonym.

The scale has a set of opposing adjectives at either end, as listed below:

alert – drowsy, calm–excited, strong–feeble, muzzy–clear headed, well-coordinated–clumsy, lethargic–energetic, contented–discontented, troubled–tranquil, mentally slow–quick witted, tense–relaxed, attentive–dreamy, incompetent–proficient, happy–sad, antagonistic–amicable, interested–bored, withdrawn–gregarious

At the specified time points during the study, subjects are asked to record how they feel at that time by making a vertical mark on the lines. Standardized instructions will be given to each subject before he completes the questionnaire. Study site personnel will check that the scale has been completed by the subject when collecting the questionnaire. The questionnaires will be evaluated using the same ruler for each subject. Date and time of collection and the distance from beginning of the line and the mark made by the subject on the VAS scale will

be recorded in mm in the CRF. If the mark occurs in between two hash marks on the ruler, the more conservative distance, ie, the longer distance will be recorded in the CRF.

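### The nicotine ban ends with the second PET scan, so a light user who resumes may have Day 9 discharge vital signs, ECG and VAS that are not comparable with his pre-treatment readings

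*Protocol*

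**What the plan says.** Exclusion criterion 7 in Protocol section 3.3.3 reads "Habitual smoker (>5 cigarettes or snuff or other nicotine products per day", so men who use up to 5 products a day can be enrolled. Section 3.3.4, item 8, then tells every subject to "Refrain from the use of tobacco or other nicotine-containing products from enrolment through completion of the last PET examination".

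Section 3.1 places the second scan as follows: "PET scanning time will be at 5-7 hours post-dose". Table 2 puts dosing at about 09:00 and the transfer back to the CPU at 7 h.

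The pre-treatment comparators are taken under the ban. For the VAS, section 4.4.4 says "The second assessment on Day 1 (pre-dose) will be the baseline assessment". For the ECG, Table 1 footnote f says "ECG should be assessed prior to first titration dose, either day -1 or day 1". Later VAS assessments are those "which will take place pre-dose on the days of dosing of SQL SR and the day of discharge from the CPU". Table 1 schedules vital signs, an ECG and a VAS on Day 9, the discharge day. No section extends the nicotine ban to discharge or prohibits nicotine in the CPU.

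Several other restrictions in section 3.3.4 last for the whole study period: enzyme-modifying drugs, liquorice and grapefruit, other medicines, alcohol, excessive caffeine, energy drinks and strenuous exercise.

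**The concern.** The study is open-label with no control group, so vital signs, ECG and VAS can be interpreted only by comparing each man with his own pre-treatment readings. That comparison is cleanest when the conditions match. Under item 8 they match through the end of the second scan and need not match afterwards.

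The Day 9 set has some value of its own. Table 1 footnote e limits Day 8 vital signs to pre-dose, so Day 9 gives the only vital signs before discharge that follow the final dose. Day 9 is also the only VAS that follows all four 300 mg doses, and the last scheduled ECG. Vital signs and VAS belong to the second secondary objective in section 2.2; ECG is a safety variable in section 6.2.1.

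If a light user resumes on the evening of Day 8 or the morning of Day 9, a nicotine effect could be read as a drug effect or could mask one. Table 1 records nicotine habits at enrolment only, so resumed use would not be captured routinely.

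**Working it through.** The protocol states no figure on this point. The check sets the end of the ban against the Panel A schedule in Tables 1 and 2.

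**End of the ban.** Dose at about 09:00 on Day 8 (Table 2) plus 7 h to the end of the scan (section 3.1) gives about 16:00 on Day 8. Table 2 calls the PET timing tentative.

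**Gap to the discharge readings.** Table 1 gives no clock time for Day 9. Assuming the readings are taken with the 24 h blood sample at about 09:00, the gap is 24 h − 7 h = 17 h.

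**Readings on each side of the ban, from Day -1 to discharge.**

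| Variable | Under the ban | After the ban, before discharge |
|---|---|---|
| Vital signs | pre-dose and 6 h post-dose on Days 1 to 7, pre-dose on Day 8: 2 × 7 + 1 = 15 sets | 1 set (Day 9) |
| VAS, excluding the training session | pre-dose on Days 1 to 8: 8 | 1 (Day 9) |
| ECG | Day -1 or Day 1, and Day 7: 2 | 1 (Day 9) |

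The Day 7 ECG follows from Table 1 footnote g, "ECG should be assessed 6 hours post-dose the third day of steady state (maintenance dose": 300 mg starts on Day 5, so the third maintenance day is Day 7.

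**Primary variables.** Both scans fall inside the ban. So does the average concentration during the scan that enters the model in section 6.1.3.1, because section 6.1.4 takes it from the start to the stop of the PET assessment.

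**Weight of one user.** With n = 3 per panel (section 6.3.4), suppose nicotine shifts one man's Day 9 reading by d. The panel's Day 9 mean then moves by d/3; with k resuming users and the same shift it moves by k × d/3, for k from 0 to 3. The protocol gives neither k nor d.

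**The case against.** The strongest reply is that nothing here is an error. Item 8 ties the ban to the scans, which carry the primary objectives, and protects them fully. Nor is nicotine singled out: in item 6 the complete PET-day ban on caffeine and stimulant drinks lapses at the same moment, moderate caffeine is allowed on other days, and occasional adrenergic nasal spray is allowed throughout. The protocol therefore never sought wholly stimulant-free safety readings.

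A near-equivalent comparison under the ban also exists. Day 8 pre-dose vital signs and VAS come about 24 h after a 300 mg dose, which is about the same interval as a morning reading on Day 9. The 6 h ECG on Day 7, at the expected time of peak concentration, is also under the ban. Any harm requires a permitted user to be enrolled, to resume while still confined, and to do so close enough to the Day 9 readings to matter. Subject listings are planned, and enrolment habits would show who the permitted users are.

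All of this stands and limits the point to something small. It does not remove the point: enrolment habits do not show whether a man resumed, and the Day 9 set remains the only one in the CPU after the final dose.

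A reader might go further and infer that the late plasma samples are compromised too. The schedule "1, 2, 3, 4, 5, 6, 7, 8, 10, 12 and 24 h post-SQL SR dose" does put the 8, 10, 12 and 24 h samples after the scan. The documents do not support that inference. Plasma is sampled only around the second PET day, so there is no nicotine-free pharmacokinetic baseline to compare with, and nothing in the protocol links nicotine to quetiapine or NDAQ concentrations.

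**Conclusion.** The point holds as a minor one. The ban ends about 17 h before the discharge readings, on the assumption of a morning assessment, and for a permitted user who resumes, the Day 9 vital signs, ECG and VAS may not be comparable with his Day -1 or Day 1 readings.

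It would be tempting to say that the end-of-treatment readings in general are not comparable with baseline. The schedule does not bear that out: 15 vital-sign sets, 8 VAS assessments and 2 ECGs are taken under the ban, against one of each afterwards. Non-comparability is also only a possibility, because it depends on someone resuming.

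The size cannot be stated beyond the weighting of one third of a panel mean per resuming user, with 0 to 3 users per panel. That nicotine affects pulse, blood pressure or self-rated alertness is assumed here; the protocol restricts nicotine but states no effect. The analysis is descriptive and exploratory, and the occupancy objectives are untouched.

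**What to change.** Change section 3.3.4, item 8, so that abstinence runs from enrolment through completion of the discharge assessments (Day 9 in Panel A). Tying it to the discharge assessments rather than to a day number also covers Panels B and C and any postponed scan.

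The cost is a few words in the protocol and less than one further day of abstinence, during which the men are still confined and compliance can be supervised. Recording nicotine use on Days 8 and 9 would be a weaker alternative: it would identify an affected reading but not prevent it. The gain is limited to the descriptive Day 9 safety readings.
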